4.3 RISKS ASSOCIATED WITH PARTICIPATION IN THE CLINICAL INVESTIGATION

There will be no additional risk for the subjects, associated with their participation in the clinical investigation. All measurements scheduled are non-invasive, without risks.

4.4 POTENTIAL INTERACTIONS WITH CONCOMITANT MEDICAL TREATMENTS

Treatment with CRYSTAL PEEL in combination with drugs and other devices has not been clinically evaluated.

4.5 STEPS THAT WILL BE TAKEN TO CONTROL OR MITIGATE THE RISKS

Risks are mitigated by including only those subjects that meet the study entry criteria.

[figure not shown]
4.6 RATIONALE FOR BENEFIT-RISK RATIO

A risk analysis documentation that identifies hazards and measures to reduce risks has been established. It is provided as an excel document and can be sent upon a request.

The figure below, represents the global risk mapping of **Crystal Peel**. It considers the different factors from conception, manufacturing process, use, transport and stockage), all associated in **Crystal Peel** risk analysis.

Each individual benefit and individual risk have been identified and evaluated according to a risk product analysis procedure. After having identified risk measures and procedures to control or to reduce these risks an overall benefit level and an overall risk level are identified.

As a conclusion the ratio of these two factors exhibits a positive benefit/risk balance.

Regarding all risks associated with the use of the Crystal Peel during the clinical investigation are identified in the Risk Analysis and are classified as minor and acceptable. We state that the Crystal Peel has a favourable benefit/risk profile.

All risks identified in the Risk Analysis are addressed in the report and considered low. A review of safety data of each excipient used in the Crystal Peel indicated low risk of possible hypersensitivity to the ingredients. Furthermore, the performance of the Crystal Peel, which is based on three combined acids which are Salicylic (20%), Mandelic (5%) and Citric acids (5%) dissolved in a mixture of alcohol-water solvent, is identified and substantiated by literature sources.

In summary, we state that the Crystal Peel is effective for the treatment of the symptoms of mild acne when the product is used according to the Instruction for Use and has a favourable benefit/risk profile due to the minimal risks associated with the use of the Crystal Peel.

5- OBJECTIVES AND HYPOTHESES OF THE CLINICAL INVESTIGATION

5.1 CLAIMS FOR CLINICAL PERFORMANCE, EFFECTIVENESS AND SAFETY OF THE INVESTIGATIONAL DEVICE THAT ARE TO BE VERIFIED

- The Crystal Peel used according to the instructions for use is successful in treating or reducing the symptoms of the mild acne for which it is intended,
- Clinical performance meets end-user needs and expectations, validating the design of the medical device,
- The benefits to patients outweigh the risks,
- The conditions of application and frequency of use are sufficient to treat mild acne.
- The objectives regarding safety and performance requirements are met.

5.2 OBJECTIVES

5.2.1 Primary objective

The primary objective of the study is to evaluate the efficacy and clinical performance of Crystal Peel, a salicylic-based peel, for the treatment of acne by lesions counting (front, 2 cheeks, the chin above the jaw line (excluding the nose)) using both visual observation and palpation.

DERMOSCIENCES FRANCE	Medical Device CIP # 22E2387	Final version 1.0 Date: 16.08.2022	Confidential Page 22/49
-------------------------	---------------------------------	---------------------------------------	----------------------------

Total lesions will be defined as the sum of inflammatory lesions (papules, pustules), non-inflammatory lesions (whiteheads and blackheads) and other acne lesions (nodules).

5.2.2 Secondary objective(s)

- Pores and texture analysis (will be performed by Newtone with Colorface acquisitions)
- Visual effect (Standardized anonymized photographs (face, 45° at left, 45° right) with Colorface)
- Investigator Global Assessment
- Patient Global Assessment
- Local and overall tolerance of the Crystal Peel, a salicylic acid-based peel, used under the normal conditions of use recommended by the manufacturer.
- Subject's self-evaluation on D78 using a questionnaire.
- Potential adverse events collection.

5.3 SCIENTIFIC JUSTIFICATION AND CLINICAL RELEVANCE

The primary endpoint of the study will be an objective counting of the acne lesions performed on every visit.

5.4 HYPOTHESES TO BE ACCEPTED OR REJECTED

Crystal Peel is effective in the treatment of mild acne.

5.5 RISKS AND ANTICIPATED ADVERSE DEVICE EFFECTS THAT ARE TO BE ASSESSED

The anticipated adverse device effects that are to be assessed are the one described in section 4.2.

6- DESIGN OF THE CLINICAL INVESTIGATION

6.1 GENERAL

6.1.1 Description of the design

The study will be:

- ◆ in open
- ◆ intra-individual
- ◆ multiple sessions of application
- ◆ single centre
- ◆ on healthy subjects

6.1.2 Description of the measures to be taken to minimize or avoid bias

Not applicable.

6.1.3 Primary and secondary endpoints with rationale for their selection and measurement

6.1.3.1 Primary endpoint

Comparison of the change from baseline of total sum of lesions on each visit- objective counting of the lesions by the investigator.

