1.5 OVERALL SYNOPSIS OF THE CLINICAL INVESTIGATION

Clinical investigation single identification #:	To be determined
Clinical investigation plan #:	22E2387
Title of the clinical investigation:	EVALUATION OF THE EFFICACY AND TOLERANCE OF CRYSTAL PEEL, A SALICYLIC ACID BASED PEEL IN THE TREATMENT OF ACNE
Sponsor:	DERMOSCIENCES FRANCE [name]
Development phase:	Post market study Confirmatory Interventional Device used according to IFU
Objectives:	
Principal aim: The primary objective of the study is to evaluate the efficacy and clinical performance of Crystal Peel, a salicylic-based peel, for the treatment of acne by lesions counting (front, 2 cheeks, the chin above the jaw line (excluding the nose)) using both visual observation and palpation.
 
Total lesions will be defined as the sum of inflammatory lesions (papules, pustules), non-inflammatory lesions (whiteheads and blackheads) and other acne lesions (nodules).
 
Secondary aims:
 
 • Pores and texture analysis (will be performed by Newtone with Colorface acquisitions) • Visual effect (Standardized anonymized photographs (face, 45° at left, 45° right) with Colorface) • Investigator Global Assessment • Patient Global Assessment • Local and overall tolerance of the Crystal Peel, a salicylic acid-based peel, used under the normal conditions of use recommended by the manufacturer. • Subject's self-evaluation on D78 using a questionnaire. • Potential adverse events collection.
Design:	Open, monocentric study with intra-individual comparisons.
Planned Sample Size:	33 included subjects for 30 results at sponsor's request
Number of investigational study sites:	1 Center in Poland

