6.4.2 Description of effectiveness parameters

6.4.2.1 Counting of the acne lesions

Investigator will perform acne lesions counting (front, 2 cheeks, the chin above the jaw line (excluding the nose)) using both visual observation and palpation on each visit (baseline, D15, D36, D57 and D78). Total lesions will be defined as the sum of inflammatory lesions (papules, pustules), non-inflammatory lesions (whiteheads and blackheads) and other acne lesions (nodules).

The change of the number of acne lesions from baseline will be calculated on each visit.

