7.2.2 Secondary endpoint(s)

- Pores and texture analysis (will be performed by Newtone with Colorface acquisitions)
- Visual effect (Standardized anonymized photographs (face, 45° at left, 45° right) with Colorface)
- Investigator Global Assessment
- Patient Global Assessment
- Local and overall tolerance of the Crystal Peel, a salicylic acid-based peel, used under the normal conditions of use recommended by the manufacturer.
- Subject's self-evaluation on D78 using a questionnaire.
- Potential adverse events collection.

Analysis of primary and secondary endpoints 'parameters':

For each continuous variable obtained from devices: A mixed linear model for repeated measurements (PROC MIXED) will be fitted to raw data.

Using the adjusted means obtained from this model (LS-Means), the contrast of interest will be built:

- To assess the change from first measurement at each time

The underlying assumptions (normality and homoscedasticity of residuals) will be checked using Shapiro-Wilk test ($\alpha=0.01$) and graphical representations.

In case of strong deviation, a transformation of the data or a non-parametric approach (Wilcoxon signed rank tests) will be performed.

The raw score will be summarized using descriptive statistics for quantitative data by time point. A Wilcoxon signed rank test will be applied to test whether the change from baseline is statistically significant.

The categorical data will be summarized in frequency (N) and percentage (%) associated with its 95% confidence interval by time point.

The questionnaire will be summarized in frequency (N) and percentage (%).

The adverse events will be analysed.

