7.3 SIGNIFICANCE LEVEL AND POWER OF PRIMARY ENDPOINT(S)

All statistical tests will be assessed at $\alpha = 5\%$ level of significance in a bilateral approach.

DERMOSCIENCES FRANCE	Medical Device CIP # 22E2387	Final version 1.0 Date: 16.08.2022	Confidential Page 35/49
-------------------------	---------------------------------	---------------------------------------	----------------------------

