7.5 PASS/FAIL CRITERIA TO BE APPLIED

7.5.1 Primary endpoint

Not applicable

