7.9 DESCRIPTION OF CONTROL PROCEDURES FOR MULTIPLICITY AND ADJUSTMENT OF ERROR PROBABILITIES

Not applicable.

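### The hypothesis has no primary visit and no decision rule, and one of the four co-equal primary comparisons comes before the first peel

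*Combined protocol and SAP*

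**What the plan says.** The synopsis (1.5) lists the study as "Confirmatory". Section 5.4, whose title announces hypotheses to accept or reject, contains one sentence: "Crystal Peel is effective in the treatment of mild acne". It names no visit, parameter or threshold.

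The primary endpoint in 6.1.3.1 is "Comparison of the change from baseline of total sum of lesions on each visit". Section 6.4.2.1 lists the counting visits as baseline, D15, D36, D57 and D78 and adds: "The change of the number of acne lesions from baseline will be calculated on each visit". In 7.2.2 the contrast of interest is "To assess the change from first measurement at each time". Section 7.3 says "All statistical tests will be assessed at" the 5% level, two-sided.

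Two sections could have supplied a rule. Section 7.9, on "MULTIPLICITY AND ADJUSTMENT OF ERROR PROBABILITIES", and section 7.5, "PASS/FAIL CRITERIA TO BE APPLIED", for the primary endpoint (7.5.1), are both marked as not applicable. Section 6.4.6 says the 78-day follow-up should allow effectiveness to be demonstrated, but it does not make D78 the primary visit.

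The first peel is at D15 (1.5). The visit list in 6.4.1.2 puts the lesion count before the peel at D15, D36 and D57. The accompanying cosmetics are handed out at D0.

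**The concern.** A confirmatory study needs a statement, fixed in advance, of which result would accept its hypothesis. Here four comparisons have equal standing and no rule combines them. Success could mean any visit, all visits, the last visit or some other pattern, and the choice could be made after open-label results are seen. The same data could then be read as success or failure.

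The D15 comparison makes this worse. A fall between D0 and a count taken before the first peel can reflect only the passage of time, entry selection on minimum lesion counts (inclusion criterion 6) and the cosmetics in use since D0, which include a 15% glycolic acid foamer for home use (6.2.2). Under the present wording such a fall could be reported as a positive primary-endpoint result before the device has been used.

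**Working it through.** **Inputs from the plan.** Four comparisons against a common D0 (6.4.2.1); two-sided 5% per test (7.3), hence 0.05/2 = 2.5% per visit in the favourable direction; 30 evaluable subjects (6.1.6). The plan gives no claim-level error rate, so there is no figure of its own to reproduce.

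**Assumed.** (a) Success means a significant fall at any one visit. (b) There is no true change at any visit. (c) The within-subject correlation over the five visits is either compound symmetry (ICC 0.3 to 0.9) or AR(1) by visit order (rho 0.3 to 0.95).

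**Correlation of the changes.** Write the change at visit j as Yj − Y0, with common variance σ².

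- Compound symmetry: variance 2σ²(1 − ρ), covariance σ²(1 − ρ), so the correlation is 0.5 whatever ρ is.
- AR(1): variance 2σ²(1 − ρ^j), covariance σ²(1 + ρ^|j−k| − ρ^j − ρ^k). For ρ = 0.7 and visits 1 and 2: (1 + 0.7 − 0.7 − 0.49)/√(0.60 × 1.02) = 0.51/0.78 = 0.65.

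**Error rate.** P(at least one favourable rejection) = 1 − Φ₄(1.96, 1.96, 1.96, 1.96; R), where R is the correlation matrix of the four changes. This was checked with 60,000 simulated trials per structure, using n = 30 and paired t-tests.

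| Structure | Correlation of changes | Four visits, favourable: formula | Four visits, favourable: simulated | Four visits, two-sided: simulated | D36, D57, D78 only, favourable: formula |
|---|---|---|---|---|---|
| Compound symmetry | 0.50 | 7.8% | 7.9–8.0% | 15.7–16.0% | 6.3% |
| AR(1) 0.3 | 0.43–0.64 | 7.5% | 7.6% | 15.0% | 5.9% |
| AR(1) 0.5 | 0.41–0.72 | 7.2% | 7.5% | 14.8% | 5.6% |
| AR(1) 0.7 | 0.42–0.79 | 6.9% | 6.9% | 13.6% | 5.3% |
| AR(1) 0.9 | 0.47–0.84 | 6.5% | 6.8% | 13.4% | 5.0% |
| AR(1) 0.95 | 0.48–0.85 | 6.4% | 6.6% | 13.0% | 4.9% |

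**Outside these structures.** Independent changes would give 1 − 0.975⁴ = 9.6%. Changes all correlated at 0.9 would give 4.7%.

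**Other readings of success, simulated.**

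- D78 alone: 4.9–5.2% two-sided and 2.5–2.6% favourable, which recovers the nominal level.
- All four visits required: 0.05–0.23% favourable.
- Any of the three visits after a peel: 9.9–12.9% two-sided and 5.1–6.4% favourable.

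**Choice of test.** Section 7.2.2 assigns the mixed model to variables obtained from devices and does not clearly say which test applies to hand-counted lesions. With the Wilcoxon signed-rank test (20,000 trials) the any-visit figures are 13.1–15.7% two-sided and 6.5–8.0% favourable, so the test makes little difference here.

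**The case against.** The plan nowhere says that one significant visit is enough. Section 7.3 promises 5% per test and nothing at the level of a claim. The 6.5–8% range belongs to an assumed rule and assumed correlations, and it includes a visit that cannot bear on the device. All of that stands: the percentages illustrate the gap and are not a property of the plan.

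A second objection is that the main threat in an open single-arm study is attribution. Time, regression to the mean after entry on minimum counts, and the cosmetics could all lower the counts. That error is not bounded by 2.5% or by 8%, and naming a visit does not remove it. This also stands. It limits what any decision rule can prove but does not excuse having none.

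Third, only the photographs are expressly placed before application (6.4.2.2). For lesion counts the order is read from the visit list in 6.4.1.2, and the flow-chart prints the peel row above the counting row. This is correct, but a count on the day of the first peel could not plausibly show benefit even if taken afterwards.

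Finally, section 3 describes the purpose as collecting performance data, and the global assessments and questionnaire fall only at D78, which points to D78 as the natural endpoint. It is still not designated. If the study is meant to be descriptive, the confirmatory label, the hypothesis and the 5% tests need to be reconciled with that.

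**Conclusion.** The concern holds. As written, the plan cannot decide its own hypothesis, and it leaves room for a pre-peel D15 fall to be reported as a primary result. That conclusion rests on the text alone.

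The size depends on the unstated rule. With no true change, the favourable error runs from below 0.3% if all four visits must improve, through 2.5% for D78 alone, to about 8% if any visit suffices. The any-visit range of about 6.5–8% (about 5–6.4% for the three visits after a peel) assumes the correlations set out in the working. This should be fixed before results are seen.

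**What to change.** 1. Name D78, the only visit after all three peels, as the single primary time point, tested two-sided at 5%.
2. Restate 5.4 in measurable terms: the mean total lesion count at D78 is lower than at D0.
3. In 7.5.1, state that the primary criterion is met if the 95% confidence interval for the D78 change from D0 lies entirely below zero. Say there which model gives the interval and in which analysis set, since 7.2 uses both ITT and PP and 7.2.2 leaves the method for lesion counts unclear.
4. Word the conclusion as a reduction from baseline under the peel plus the accompanying cosmetics in an open, uncontrolled study. The plan gives no clinically relevant reduction, so if relevance is to be claimed the sponsor must prespecify and justify a threshold.
5. In 7.9, test D57 and then D36 in fixed sequence only if D78 is significant, or report them descriptively with confidence intervals. Either keeps the favourable error at 2.5%. Keeping an any-visit rule would instead need one-sided 0.025/4 = 0.00625 per visit, or 0.025/3 = 0.0083 for three visits.
6. Remove D15 as an efficacy test and report it as the pre-peel value. Add D78 minus D15, with its interval, as a supportive contrast that leaves out the 15-day pre-peel phase.
7. Label secondary p-values as supportive and unadjusted.

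The cost is protocol wording only, with no extra subjects, visits or data. The downside is that a result at an earlier visit could no longer support the claim by itself.

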6.1.3.2 Secondary endpoints

1. Pores and texture analysis – analysis using Colorface photographs: For pores analysis: front face image and PP polarization; For texture analysis: profiles images and CP and Std 60 polarization.
2. Visual effect - Colorface photographs
3. Investigator Global Assessment score
4. Patient Global Assessment score
5. Local and overall tolerance of the Crystal Peel
6. Subject's self-evaluation on D78 using a questionnaire
7. Adverse events number

6.1.4 Method and timing for assessing, recording, and analysing variables

Procedure (time-points)	V1	V2	V3	V4	V5
Intervals	D0	D15 (+/-1)	D36 (+/-2)	D57 (+/-2)	D78 (+/-3)
Checking the inclusion/non-inclusion inclusion/non-inclusion criteria	●				
Physical examination/Vital signs / medical history and treatment	●				
Informed Consent Form	●				
Pregnancy test	●				
Exclusion criteria	●	●	●	●	●
Use of associated treatment		●			
PEELING ACT					
Colorface Standardized Photos (X3)	●	●	●	●	●
Lesions counting	●	●	●	●	●
pores analysis by Newtone	●	●	●	●	●
texture analysis by Newtone	●	●	●	●	●
Local tolerance		●	●	●	●

Procedure (time-points)	V1	V2	V3	V4	V5
Intervals	D0	D15 (+/-1)	D36 (+/-2)	D57 (+/-2)	D78 (+/-3)
Dispense cosmetic products and daily log	●				
Collect daily log		●	●	●	●
Subjective evaluation questionnaire					●
IGA					●
PGA					●
Adherence control, record of AE, concomitant treatments	●	●	●	●	●
End of study form					●

6.1.5 Equipment to be used for assessing, recording and analysing variables and arrangements for monitoring maintenance and calibration

The device used for the photographs taking will be the Colorface®. The maintenance of device used for the clinical investigation were checked before study beginning. The calibration of these devices (by the technician) is done regularly.

6.1.6 Procedure for the replacement of subject

Subjects will not be replaced. It is planned to include 33 subjects to reach 30 evaluable subjects.

6.1.8 Definition of completion of the clinical investigation

The investigation will be completed after the last subject last visit.

6.2 INVESTIGATIONAL DEVICE

6.2.1 Description of the exposure to the investigational device

6.2.1.1 Dosage

2,5 ml of Crystal Peel applied with cotton bud. Application of 2,5 ml of the product in 3 layers.

6.2.1.2 Instructions for use

- 1 | CLEANSE

Cleanse the face using 4 pumps of Foamer 15, rinse and dry.

- 2 | PEEL APPLICATION

Pour 2.5 ml of Cyrstal Peel into a cup and apply to the face using 1 cotton bud. Apply with vertical and horizontal strokes across all areas. Always start by applying the product on the T-Zone, followed by the jawline and mouth, and finish with the cheeks. Apply up to 3 layers, waiting for 1 minute between each layer. Leave the last layer up to 5 minutes, whilst observing skin reaction. Rinse abundantly with water and dry the face. Remove immediately in case of intense reaction or pain.

6.2.1.3 Precautions for use

For external use only and for use on a limited area, due to the presence of Salicylic Acid. For adults only.

- Skin preparation is recommended 15 days before the first peel.
- Must only be used by trained healthcare professionals. Required knowledge of complications associated with the application of medical devices and how to react is necessary.
- Always use protective gloves during the procedure and clean the glass cup carefully between each peel session. Cotton buds should be disposed of after each use.
- Do not use alcohol or acetone-based cleanser.
- Avoid the lip area and nasolabial folds. Do not swallow.
- Avoid eyes and mucous membranes: in the event of accidental contact, rinse thoroughly with water, and use a saline solution.
- Avoid sun exposure and use sun protection (K Ceutic or Sun Ceutic 50+) for 4 weeks after the treatment and in-between treatments.
- Keep out of the reach of children.
- In case of alteration in the product's appearance, do not use the medical device.
- Protocol variations should be based on assessment of patient skin type, treatment tolerance and desired results.
- Do not apply on a large area or other areas of the body to avoid a high absorption of Salicylic Acid.
- Never hold the medical device above the patient to avoid accidental spillage.
- If an allergic reaction is considered likely, apply the product to a 1 cm² sized area behind the ear, following the exact same protocol. If no unusual reaction is observed within 72 hours, the facial peel can go ahead.

The practitioners are asked to refer to the last version available of IFU/IB.

6.2.2 List of other medical device or medication to be used during the clinical investigation

No other medical device or medication is planned to be used according to the CIP. However the associated cosmetic products are to be used during the investigation.

Accompanying products are commercially available products developed by DERMOSCIENCES LTD. They are used to prepare and protect the skin during the peeling procedures and to maintain the effect of the peeling.

Foamer 15 (15 % glycolic acid foamer):

- Use as a pre-peel: Cleanse the face with 4 squeezes spread over the whole face, rinse thoroughly after 2 minutes or as soon as the first tingling appears and dry.
- Use at home: Apply a small amount of foam to the clean and dry face.

Massage and rinse with water after two minutes or as soon as you start to feel tingling.

- Precautions: You may feel a tingling sensation. If discomfort occurs, reduce the frequency of use.
- Do not apply to irritated or damaged skin, or to the eyes and mucous membranes.

Avoid exposure to the sun.

Hyal Ceutic (Intense moisturizing cream):

- Use: Apply when skin needs moisturising, all over the face during the day as required.
- Precautions for use: Avoid contact with eyes and mucous membranes. In case of contact, rinse with plenty of water. Do not apply to open wounds.

Sun Ceutic teintée (SPF 50+ product, slightly tinted):

- Use: Every morning, apply evenly to the face, neck and décolleté 10 minutes before sun exposure. Reapply frequently.
- Precautions for use: Do not apply to irritated or damaged skin, or to the eyes and mucous membranes. In case of contact, rinse with plenty of water. Avoid prolonged exposure to the sun, even with the cream.

DUAL+ (Night cream):

- Use: Apply in the evening to the full face focusing especially on the areas of concern. Increase frequency progressively, up to 2 times per day.

PRECAUTIONS You may experience a tingling sensation, redness and slight desquamation. In case of discomfort, reduce the frequency of use.

DERMOSCIENCES FRANCE	Medical Device CIP # 22E2387	Final version 1.0 Date: 16.08.2022	Confidential Page 26/49
-------------------------	---------------------------------	---------------------------------------	----------------------------

Do not apply to irritated or broken skin. Do not combine this product with other retinol-based products. Avoid direct contact with eyes and mucous membranes.

During use, avoid exposure to sunlight without high SPF protection.

Not recommended for sensitive and/or very dry skin.

NB: All these cosmetic products are in the market

